Appendix II: Progression criteria from internal pilot

Project implementation

Area	Question	Assessment	Criteria	Rag rating
Therapist Recruitment	Have sufficient therapists been	Number of therapists recruited	7	>6 in post
	recruited			<6 >4 in post
				<4 in post
Therapist Training	Have sufficient therapists been	% of therapists certified	75%	>75%
	certified			60 – 74%
				<60%
Therapist Supervision	Do therapists attend planned supervision	% of therapist supervision sessions attended	75%	>75%
				60 – 74%
				<60%
Therapist Capacity	ls there sufficient capacity to provide MDFT Is there sufficient capacity to provide capacity Model of randomisation/ capacity		100%	100%
			90-99% increase number of therapists by 1	
				<90% increase number of therapists by required number
			80%	>80%

Dosage within 4-6 months 55% adolescent sessions 30% family sessions 15% parent alone sessions	Do participants comply with the minimal dose of MDFT	% participants receiving minimal dose		60-79% <60%
Eligible referrals	Are sufficient referrals eligible	% of eligible participants who consent	80%	>80% 50 - 79% <50%
Acceptability of adaptions	Are the adaptions to MDFT acceptable to therapists and participants	Review of adaptions	Adaption should be acceptable	Acceptable to some but not all revise adaption Not acceptable

Internal pilot evaluation

Area	Question	Assessment	Criteria	Rag rating
Participant recruitment	· ·	60	60	
				42-60
				<42
Evaluation attrition	aluation attrition Have sufficient % of participan participants been retained		90%	>90%
				70 – 89%

	retained at 6- months			<70%
Proportion with primary outcome	Have sufficient participants	% of participants completing primary	95%	>94%
recorded at month	provided a primary outcome	outcome		75 – 94%
				<75%%
Proportion with secondary outcome	Have sufficient participants	% of participants completing	80%	>80%
recorded at month 6	provided a secondary	secondary outcome		60 – 79%
	outcome			<60%
Analysable primary and secondary	secondary participants who providing usefull	providing usefull primary and secondary	80%	>80%
outcome data				60 – 79%
		outcomes		<60%
Randomisation	Are the groups allocated to MSFT and BAU of similar size	Difference in the proportion allocated to each group	2%	<2%
				3-5%
				>5%
Randomisation	Are the groups allocated to MSFT	Difference in the proportion allocated to each group by	5%	<5%
	and BAU of similar size by stratification			5-10%
stratific		stratification		>10%

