- ERQ13 To conduct a latent class mediation analysis to explore how the volume of violent offences is mediated by the frequency and type of substance used at 6 and 12 months.

Part of this work will be to examine the potential impact of both UK and region-specific issues that may be linked to race, ethnicity, sex, socioeconomic factors and other considerations that may arise which are connected to EDI.

Internal pilot study

Prior to embarking on the efficacy study an internal pilot study will be undertaken. The aim of the internal pilot study is to explore whether it is feasible to deliver MDFT in the UK context and establish key parameters to incorporate into the design of the efficacy study. Progression criteria are detailed in appendix II and the study will be conducted between September 2025 with a transition decision in June 2026.

In the pilot study we will recruit 60 participants, 30 in each arm, across the 2 sites. This will allow for exploration of key parameters needed to confirm sample size calculation for the efficacy study. It is sufficient to allow estimation of two-sided 95% CIs around the proportions of eligible, consenting, adhering and followed up at month 6 in each arm of the study with half-widths less than 0.15. It meets the 30 per group recommended by Lancaster et al (Lancaster et al., 2004) for estimating the SE of a primary outcome with sufficient precision, including accounting for any variation across site, where 12 participants per arm per site is recommended.

Objectives for the internal pilot trial

- **PRQ1** To conduct a prospective, two-arm, individually randomised RCT to pilot study outcomes and methods and establish the parameters for the conduct of efficacy evaluation.
- **PRQ2** To assess whether progression criteria have been met and develop an appropriately powered efficacy protocol.
- **PRQ3** To confirm the pre- post-test correlation on the primary outcome, percent days abstinent from alcohol and/or drugs to incorporate into a sample size calculation.
- **PRQ4** To estimate an estimate of potential effect for the primary outcome for inclusion in a sample size calculation.
- PRQ5 To explore the relationship between the use of alcohol and specific drugs and violent offending. This will be achieved through an analysis of existing datasets; Reframe and RISKIT-CJS, with a confirmatory analysis conducted on the pilot data at the time of transition.

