primary outcome	measure (instrument, scale, source)	Single substance use question assessing the 28 days prior to baseline.		
Baseline for secondary outcome	variable	Volume of self-reported offending in the 6 months prior to baseline. Behaviour: internalising behavior and externalising behaviour at baseline. Mental health and wellbeing at baseline. Family cohesion and conflict at baseline. Alcohol and substance use problems at baseline. Self-report Client Service Receipt Inventory (CSRI) in the 6 months prior to baseline to assess police involvement (arrests, cautions, charges, court attendance), educational outcomes (suspensions, exclusions, managed moves) and employment status.		
	measure (instrument, scale, source)	Offending: Self-report delinquency questionnaire covering the previous 6-month (SRDS).		

Behaviour: Strengths and difficulties questionnaire (SDQ). internalising behaviour and externalising behaviour.

Mental health and wellbeing, Warwick-Edinburgh Wellbeing Scale-short form (WEMWBS-SF).

Family: Brief Family Relationship Scale (BFRS).

Alcohol and substance use problems, European School Project on Alcohol and Drugs Problem Scale (ESPAD-PS).

Self-report Client Service Receipt Inventory (CSRI).

Randomisation

The randomisation of young people to MDFT or BAU will be conducted by research staff after informed consent has been taken and the baseline assessment completed, by intake staff at Barnardo's. The allocation will involve an equal probability of receiving one of the two trial arms, MDFT or BAU, and will employ random permuted blocks of variable size (2, 4 or 6) with a random block seeded throughout. Randomisation will be conducted using a secure, independent randomisation service, Sealed Envelope Ltd. Randomisation will be stratified by geographical site (Bristol, Newport) and severity of substance use (low/ medium, high) ascertained using the GAIN-SS assessed at baseline. A full quality assurance AUDIT trail will be kept of all allocations and research staff will not be able to see future allocations. The allocated group will be relayed back to staff in the sites.

It is not possible, or appropriate, to blind young people or staff to their allocated group although follow-up at months 6 will be conducted by researcher's blind to participant allocation.

Participants

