Trial does not recruit to target	The process of recruitment is an outcome of interest in a pilot study rather than a threat to validity. We will monitor key recruitment criteria and explore, through qualitative interviews key barriers and facilitators associated with recruitment, ensuring that lessons learnt are incorporated within the efficacy study. The evaluation team have extensive experience of recruiting participants in RCT's involving substance using adolescents and have consistently achieved recruitment targets.

Not recruiting sufficient therapists to deliver MDFT may impact on recruitment in the trial.	We have allowed for a three-month lead in to recruit therapists for the trial. Barnardo's has demonstrated experience in recruiting specialist staff to deliver specialist interventions in the target sites and have key contacts with organisations within the community to identify staff.
Trial does not retain sufficient participants at the final end point	We estimate 90% of eligible and consenting participants will be available at the 6-month endpoint, a figure to be reviewed at the end of the pilot study. Evaluation staff have multiple strategies for retaining young people in research studies including payments for outcome completion, collection of multiple contact methods and the use of co-locators. In other studies, involving similar populations the target retention rate has been achieved and, in some cases, exceeded.
Therapists not retained.	Therapist retention will be monitored in the MDFT group at both sites. Barnardo's have specific strategies to retain staff and as MDFT is not delivered currently within the UK opportunities for staff to move to new services are limited.
The random nature of selecting young people could be seen by some as unethical.	we are in a state of equipoise regarding the effects of the intervention. Control group participants will receive established BAU that is current practice in accordance with the Declaration of Helsinki. No participant will be disadvantaged by being allocated to BAU.

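### Several Appendix II progression thresholds do not work as written: on-target values fall between bands, eligibility has no threshold, the primary-outcome row has no denominator, and the balance rows penalise correct randomisation

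*Protocol*

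**What the plan says.** The Protocol section on the internal pilot states: "In the pilot study we will recruit 60 participants, 30 in each arm, across the 2 sites". Under Randomisation, allocation uses "random permuted blocks of variable size (2, 4 or 6"), and "Randomisation will be stratified by geographical site (Bristol, Newport) and severity of substance use (low/ medium, high"), which makes four strata.

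Appendix II then sets the bands:

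- **Evaluation attrition:** criterion 90%; green >90%, amber 70 to 89%, red <70%. The Risks table gives the planning value: "We estimate 90% of eligible and consenting participants will be available at the 6-month endpoint". The sample size section likewise assumes 10% loss.
- **Primary outcome recorded:** criterion 95%; green >94%, amber 75 to 94%, red <75%. The measure is the percentage "of participants completing primary" outcome, with no denominator stated.
- **Eligible referrals:** the question is whether enough referrals are eligible. The measure is the percentage "of eligible participants who consent", with criterion 80%.
- **Randomisation, overall:** "Difference in the proportion allocated to each group"; green <2%, amber 3 to 5%, red >5%.
- **Randomisation, by stratification:** the same difference; green <5%, amber 5 to 10%, red >10%.

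The pilot analysis section says the proportions eligible, consenting and followed up will be estimated and each compared with the progression criteria. It points to Appendix I for those criteria, but they are in Appendix II.

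**The concern.** The ratings feed the June 2026 transition report. A useful criterion should rate every possible result, measure what its question asks, and react to poor conduct more than to chance. Several rows fail one of these tests. A pilot that performs exactly to plan could be unrated on retention, amber on the primary outcome, and amber or red on balance. Meanwhile the eligible share of referrals, on which the recruitment forecast depends, has no threshold of its own.

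**Working it through.** **Plan's own figures.** Effect 0.27, correlation 0.4, two-sided alpha 0.05, power 80%. Residual SD = √(1 − 0.4²) = 0.917. Per arm n = 2 × (1.960 + 0.842)² × 0.84 / 0.27² = 180.9, so 181 per arm and 362 in total, against 364 stated: reproduced. 364/400 = 91% retained, close to the stated 90%.

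**1. Gaps between bands.** 54/60 = 90.0% meets the criterion but is neither >90% nor within 70 to 89%. Binomial(60, 0.90):

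| Result | Rating | Probability |
|---|---|---|
| 55 or more | green | 0.44 |
| exactly 54 | none | 0.17 |
| 42 to 53 | amber | 0.39 |

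The same gap occurs at:
- exactly 80% in the dosage, consent, secondary-outcome and analysable-data rows (for example 48/60);
- exactly 75% in the therapist certification and supervision rows;
- 6 or 4 therapists, because the bands are >6, <6 and >4, and <4.

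**2. Eligibility row.** Question and measure differ: one concerns eligible/referred, the other consenting/eligible. No other Appendix II row has eligible/referred as its measure. Table 2 plans 500 referred and 400 recruited, and 400/500 = 80%. That equals the assumed consent rate alone, so the forecast appears to leave no allowance for ineligible referrals.

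**3. Primary-outcome row.** Green at n = 60 needs 57 (57/60 = 95.0%; 56/60 = 93.3%).

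- *All randomised as denominator.* Completion cannot exceed retention. At 90% retention with every retained participant completing, the expected count is 54/60, which is amber. P(57 or more) = 0.14, an upper limit; at 91% retention it is 0.20.
- *Those retained as denominator.* The two rows are compatible, but meeting both targets gives 0.90 × 0.95 = 85.5% of those randomised, and 0.855 × 400 = 342. Power at 342 (171 per arm): standardised difference 0.27 / (0.917 × √(2/171)) = 2.72, giving 77.5% by the t-test, against 80.0% at 364.

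**4. Balance rows.** With 60 participants the overall difference can only be:

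| Split | Difference | Rating |
|---|---|---|
| 30:30 | 0% | green |
| 31:29 | 2/60 = 3.3% | amber |
| 32:28 | 4/60 = 6.7% | red |

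Green therefore requires perfect balance. Unfinished blocks in four strata make small imbalances normal. Correct randomisation was simulated with 60 participants, a 60/40 site split (as the Protocol expects), blocks of 2, 4 and 6 equally likely (assumed), and 30 to 70% high severity (assumed, because the Protocol gives no split):

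- Overall row: green about 41%, amber about 48%, red about 11%. With cell sizes fixed at 18/18/12/12, red is 7.5%.
- By-stratum row, site and severity rated separately: at least one red in 14% (50% high severity) to 25% (30% or 70%).
- By-stratum row, each of the four cells rated: at least one red in 50% to 71%.

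**The case against.** Several stronger readings are tempting, and the Protocol does not support them.

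- *Eligibility is never measured.* It is: the pilot is sized partly to estimate the proportion eligible, and the pilot analysis section reports it. What is missing is a threshold.
- *A shortage of eligible referrals would go unnoticed.* It would probably show in the participant recruitment row, which turns red below 42. That row cannot separate poor eligibility from low referral volume or refusal, but it would give a warning.
- *Correct randomisation usually scores red overall.* It does so in about 1 pilot in 10, and almost never if the difference means deviation from 50%. The wording favours a difference between groups, and the main fault of the row is that green is so hard to reach. The 50 to 71% figure applies only if all four cells are rated, which the row does not say.
- *The 95% target contradicts 90% retention.* This depends on the denominator. Retention is a separate row, so completion among those followed up is a plausible reading, and its cost is small: about 2.5 points of power. Exactly 90% retention would itself give 360, not 364.
- *Recruiting 60 is both green and amber.* The recruitment row is damaged in the available text, and a lost symbol cannot be excluded. No weight is placed on it.
- *One red row stops the trial.* No rule says how rows combine, so an amber or red row with an innocent explanation need not block progression.

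The gaps at exact boundaries are also simple to repair. What stands is that the Protocol itself fixes these thresholds. They are not detail left to a later analysis plan, and as written they leave planned performance unrated or penalise it.

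**Conclusion.** The point holds in this limited form. The band gaps and the mismatched eligibility row follow directly from the text and need no modelling beyond the 17% probability, which assumes independent participants and true retention of 90%. The primary-outcome row is undefined. One reading makes green unlikely for a pilot on plan (at most about 14%), and the other lets a pilot pass at a rate that would deliver 342 rather than 364 (power about 78%). The overall balance row misses green in about 59% of correctly randomised pilots. The by-stratum figures are a range, because both the unit rated and the severity split are unspecified. The table should be corrected before the transition assessment. Nothing here shows that the design of the main trial is unsound or that the pilot would wrongly be stopped.

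**What to change.** Revise Appendix II as follows.

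1. Make every band contiguous: at or above target; from the lower bound to below target; below the lower bound. Apply this to the therapist count as well.
2. Split the referral row into percentage of referrals eligible and percentage of eligible consenting, each with its own threshold.
3. Define primary-outcome completion over all randomised, and use one green cut-off for it and for retention. Choose 91% (364/400) or 90% (if the planned 10% loss is kept), but not one for each row, which would recreate the inconsistency. At n = 60 these mean 55 or 54 participants. Even then, a pilot with true retention of 90% reaches 54 or more with probability 0.61, so an amber result is ordinary sampling variation and should be read with its confidence interval.
4. Replace the two balance rows with a check that every allocation matches the randomisation service's list.
5. Correct the Appendix I cross-reference in the pilot analysis section.

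The cost is one table and one cross-reference. No new data are needed.

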Appendix III: Equality Impact Assessment

The template form includes a comprehensive list of themes to consider in our approach to race equity diversity and inclusion across YEF projects. However, not all sections of this form will be equally relevant to all projects. Please agree which sections are focus areas for your project team to complete with the relevant project lead.

Section 1 - Overview						
Name of grantee	[name]		Name evaluator	of	University of Kent	
Name of project	Multi-Dimension	nal Family The	erapy (MDFT)			
YEF PM			YEF EM			
Section 1b – YEF revie	w					
Reviewed by Race Equity Associate		Yes □ No □				
Do you recommend that we approve this EQIA?		☐ Yes ☐ Yes — with conditions ☐ No				
Narrative supporting the	recommendation					
Section 2 – Evaluation details						
Type of evaluation		☐ Feasibili☐ Pilot (pr	-			

	□ Efficacy
	☐ Effectiveness
Research question	Does Multidimensional Family Therapy reduce alcohol and drug use in adolescents.
Research design	Mixed method, individually randomised controlled trial with embedded internal pilot.
Research location	Newport and Bristol
Research period	April 2025 – March 2028
Number of participants	400
Characteristics of participants	Young people aged 13-17 years who are at risk of offending due to substance use or have offended and are involved with CJS. Screen positive for a substance use disorder. Resident within the research areas, Bristol & Newport. 'At risk of offending' is defined as having at least one of the following risk factors, assessed on referral. Previously being in the secure estate. Currently, or previously, persistently absent from school (defined by DfE as 10% or more). Have been the victim of violence. Currently, or have attended alternative education provision. Received at least one suspension from school. Have a sibling or parent who has been involved in serious violence or identified as facing exploitation harm. Currently, or have been, in the care system. Have been identified as being at risk of criminal exploitation.

Are engaged with the Supporting Families Programme. Currently or have had a social worker. Have previously been in contact with youth justice services.

Have been arrested and released by the police with no further action.

Participants must evidence alcohol or substance use on at least 4 occasions in the past 28 days, assessed using a single substance use frequency question and be willing and able to provide informed consent or willing to provide assent with a parent/ carer willing to provide consent.

Short term outcomes

Short term outcomes are measured at baseline and again at 6-months post-randomisation.

Key aims and benefits of the research

Changes in the frequency, quantity and type of substances is assessed using the time line follow-back method over a 90-day retrospective period (TLFB90; (Sobell and Sobell, 1995). Violent, non-violent and antisocial behaviour is assessed using the selfreport delinquency scale (SRDS; (McAra and McVie, 2007). Emotional regulation, internalising, externalising and prosocial behaviours, and conduct issues are assessed using the strengths and difficulties questionnaire (SDQ; (Goodman, 1997)). Wellbeing and mental health are assessed using the Warwick Edinburgh mental wellbeing scale (WEMWBS; (Clarke et al., 2011)). The frequency of school attendance, exclusion, suspensions and involvement with the police and criminal justice system is assessed using a short form client service receipt inventory validated in other studies of adolescent substance using populations (CSRI; (Coulton S et al., 2023, Coulton et al., 2024)).

Long term outcomes

Long term outcomes occur beyond the horizon of the trial. They are considered as longer-term impacts associated with changes observed in the short-term outcomes. Sustained reductions in substance use. Greatly reduced violent and non-violent offending due to reductions in risk factors associated with offending behaviour and fewer externalising and conduct behaviours. Improved educational attainment due to reduced absenteeism and less disengagement with education leading to increased propensity to remain in education or transition to employment. Improved physical and psychological health due to reduced substance use and fewer internalising behaviours and a more positive transition to adulthood.

The proposed research is to explore the adaptation of MDFT for young people and families in the UK, regardless of their background or self-identification as belonging to any group whereby their protected characteristics would suggest belonging to any marginalised group by virtue of such characteristics.

Previous equality related research or consultation relevant to this research

As can be seen below, a consideration of previous relevant research pertaining to equality has been included as it relates to the individual characteristics of potential participants. This has been done to aid consideration of these issues in turn. The importance of intersectionality is also considered throughout this assessment, and this will be explored in further detail in the section entitled 'Summary of the main equality issues'.

In preparation for the completion of this EIA, consultation with a group of young people has been ongoing where consideration of key equity-related issues have been discussed. To augment

	these discussions, two members of this group have also been involved in helping to prepare this document.	
Section 3 - Identify who from the protected characteristic groupings or other relevant disadvantaged communities will or may be affected and how		
	☑ Positive impact	
	☐ Negative impact	
	☐ No impact	
	☐ Impact not known	
Age	Narrative: The research study and delivery of the MDFT intervention is likely to have a positive impact on participants of all ages, but particularly those individuals eligible to take part according to their age (13-17). However, as MDFT also includes family members/carers/appropriate adults that are associated with the young participants in question, this research study is also likely to have benefits for individuals outside of the 13-17 age bracket of young people. Given the range of outcomes it seeks to address, if effective, the impact of MDFT could extend beyond youth violence and be a part of government efforts to improve outcomes for vulnerable children, including through the Family Hubs initiative and the response to the Care Review.	
	Through consultation with young people as part of the codesign process, questions were asked about the freedom of young people under the age of 16 to take part in the study if their parents or carers were opposed to the idea, and if a lack of parental/carer support would be a barrier to their taking part.	

Mitigation: Regarding young people's concerns, the involvement of a specific adult is not required for participation in the study. This is because 'family' involvement could be an adult other than a parent/carer with involvement in the young person's life. Initial sessions of MDFT are often directed at identifying such an adult who is then able to provide consent for continued involvement in the study. □ Positive impact
 □ Positive im ☐ No impact Narrative: Overall, it is expected that the impact of the study on participants identifying as having a disability will be positive. This is expected to be particularly true of individuals who are experiencing issues surrounding their mental health, as the process of engaging in MDFT has been shown to improve mental health outcomes for those experiencing a range of mental health issues, even in instances of comorbidity (Liddle, Disability 2016). A further positive impact of the proposed research is that participants will not only have the opportunity to access MDFT, but also to reflect on this process with the evaluation team afterwards, thus providing a further opportunity to examine their participation and have their voices heard about the future development and implementation of the intervention. This is true both of recipients of MDFT and the delivery team. As with many research projects of this nature, there is the potential for negative impact for those whose specific disabilities may make it more difficult to access this kind of study. Furthermore, for those experiencing mental health

difficulties, there is the possibility that both sessions and interviews may prove challenging. Mitigation: To mitigate any potential negative impact, it is essential that any and all reasonable adjustments to the delivery and evaluation process of MDFT are made to ensure that equitable participation is possible for all participants, regardless of their disability status. This will be achieved through the development of both sensitivity and safeguarding protocols for participants and a focus on appropriate signposting for all participants. □ Positive impact ☐ Negative impact ☐ No impact Narrative: Research has shown that adolescence is a period in which one's sexual identity is often uncertain and that furthermore that this can be made especially challenging in connection with a range of wider social determinants (Moore and Rosenthal, 2007). **Sexual orientation** However, there is evidence that also suggests that MDFT can help to navigate these issues and provides a positive space in which to negotiate the complex relationships between adults and young people as they transition from adolescence into young adulthood (Liddle et al., 2024b) Mitigation: Whether or not the UK specific context of the study will also allow positive interactions to develop when encountering issues around sexual orientation and identity is largely unknown at present, but the evaluative process will

provide an opportunity for all participants to explore this notion. Additionally, the training provided to all delivery staff will make them both aware and well-equipped to deal with such issues within a safe therapeutic environment. Individual sessions held with young people will also afford the opportunity to discuss anything that young participants may feel uncomfortable speaking about with their family/appropriate adult which can then (depending on the wishes of the young person in question) be introduced in a safe and supportive environment. □ Positive impact ☐ No impact ☐ Impact not known Narrative: The over-representation of individuals belonging to marginalised ethnicity groups within youth justice settings is a global issue, and so too is this the case in the UK (Van den Brink, 2022). Similarly, there are marked differences in outcomes across a wide range of health and social indicators that are directly linked to the ethnicity or race of individuals. As part of Ethnicity the study is to explore the adaptability of the MDFT intervention to the UK context and as such will examine any barriers or facilitators to access and engagement of the MDFT intervention, such barriers if encountered can be identified through evaluation and addressed – leading to positive future outcomes. There may be the possibility of a negative impact for those potential participants whose first language is not English when engaging with either the intervention or evaluative interviews as part of the project, even if this is a reduction in efficacy of communication linked to needing to use one's non-native language.

Young people consulted as part of this process raised concerns around engaging with therapists or researchers that were of different ethnicities or cultural backgrounds, as they felt that this may lead to a lack of understanding of the issues that they faced. This was highlighted by several young people from a variety of backgrounds. When the notion of training and education for all prospective staff was discussed, many of the young people expressed that this would help to form the trusting relationships required for such a process to work. They were however keen to point out that they felt using the phrase 'cultural competency' suggested that one could attain a level or 'certificate' in this area, when this was only something that would work with a sustained and ongoing interest and willingness to learn about the experiences of individuals from other ethnic and cultural backgrounds. This move away from the notion of 'cultural competency' is something that is echoed in relevant research literature (Fisher-Borne et al., 2015).

Mitigation: Data around those individuals who both do and do not engage or continue to engage will be collected throughout the project to be able to identify any trends within groups. Should it be necessary, the research team will explore any access needs (availability of further tailored resources etc.) that may be required moving forward. The intervention provider, Barnardo's has experience in recruiting, training and retaining interventionists who are representative of the ethnic diversity of the areas they serve.

As stated above, the introduction of culturally relevant and sensitive training to individuals on the research and delivery teams were welcomed by young people, but with the caveats described above.

	□ Positive impact □
Sex	☑ Negative impact
	□ No impact
	Narrative: Previous studies of MDFT have indicated that it is an
	effective treatment for substance use in both male and female participants (Greenbaum et al., 2015) and thus there is the likelihood of a positive impact in this regard.
	In the UK, female involvement in crime (particularly for young people) is still not as well understood as that of their male counterparts. Despite accounting for 13% of proven youth offenses is 2022, their involvement in violence remains largely invisible and support services are rarely specifically catered to girls and young women (Local Government Association, 2024).
	Due to the nature of identification of eligibility for the study and the referral pathways thereof, there is the possibility that young women and girls that may benefit from involvement in the study could be missed through the ways in which eligibility is defined.
	Mitigation: Although some areas of eligibility may lead to an under-representation of female participants in the study, when all criteria are taken into account, it is felt that this risk is sufficiently minimised through multiple points of identification for eligibility and inclusion in the study. Moreover, delivery teams will work closely with organisations that currently work with prospective participants to fully explain the process and support them where necessary to aid them.
Religion or belief	
	□ Negative impact □ Negative im

□ No	impact	
------	--------	--

Narrative: Despite research investigating the link(s) between religion/belief and substance use more generally (Weinandy and Grubbs, 2021) a consensus as to the role that religion and belief play in the appearance of substance use disorders remains unclear. Critics of current research point to a lack of an agreed upon definition of religious belief and how this is measured (Rew and Wong, 2006), as well as conflicting approaches to the inclusion of spiritual (but not necessarily formal) beliefs (Galanter et al., 2024).

In the UK context, it is worth noting that individuals from the Muslim community report a significantly negative perception and experience of formal and structured counselling services, with a survey conducted by the Lantern Initiative finding that 1 in 5 people felt judged or dismissed as a Muslim when attending such services (Woolf Institute Centre for Mental Health, 2024).

Young people involved in the consultation that identified as belonging to non-Christian religious communities also stated that they would have possible concerns about the discussion of cultural or religious norms if there was the possibility that these may clash with the theory underpinning the therapeutic intervention. This worry was more acute if these issues were raised in sessions with parents/carers. Broadly speaking, some of the concerns raised in connection with religion and belief were similar to those highlighted in discussions around ethnicity and cultural considerations detailed above.

Mitigation: Working with religious communities in a way that makes them feel both seen and heard and values the importance of their beliefs is of paramount importance to

ensure equitable access to the study. To achieve this, close working and an iterative approach to delivery and evaluation will be required. Both delivery and evaluation teams will undergo training and guidance to ensure they are confident in delivering their tasks in a culturally sensitive and aware way. This will also be monitored through regular consultation with an equity advisory group when formed. ☐ Positive impact □ Negative impact ☐ No impact Narrative: There is a general paucity of literature pertaining to non-binary gendered individuals and both alcohol and substance misuse. However, where studies do exist, evidence suggests that individuals identifying as non-binary experience higher prevalence of alcohol and substance use compared to other groups (Meads et al., 2023). **Gender reassignment** The current situation in the UK – especially for young people – for transgender individuals is one characterised by the problematisation and pathologisation of childhood gender diversity and an environment in which both gender diverse young people and their parents/carers feel increasingly isolated (Rickett et al., 2024). This feeling of isolation is especially pronounced when engaging with health service providers (Horton, 2022). Mitigation: Additional care in involving non-binary gendered participants and their families/carers will need to be taken

throughout the intervention and evaluation process, taking into account that trust may be more difficult to develop. Knowledge of issues currently facing non-binary or transgendered individuals will be of importance and further work as part of the project will need to be conducted to measure any potential impact as this is currently largely unknown.				
☐ Positive impact				
☐ Negative impact				
☑ No impact				
☐ Impact not known				
Narrative: It is anticipated that the impact on individuals in this group is likely to be neutral (no impact).				
Mitigation:				
☐ Positive impact				
☐ Negative impact				
⊠ No impact				
☐ Impact not known				

	☑ Positive impact
	☐ Negative impact
	☐ No impact
	☐ Impact not known
Social class	Narrative: Studies have previously shown that social class and socioeconomic status can lead to an over-representation of individuals from lower income groups across a number of the inclusion criteria for the proposed study (Sosu et al., 2021). Furthermore, the impact of factors such as persistent absenteeism at school have also been demonstrated to have significantly more detrimental effects when coupled with socioeconomic factors and the presence of mental health conditions (Wickersham et al., 2021). As such, the research project is expected to have a positive impact on mitigating the impact of such adverse impacts upon those participants currently experiencing inequality and inequity that is related to social class/socioeconomic status.
	Mitigation:
	☐ Positive impact
	☐ Negative impact
	⊠ No impact
Other	☐ Impact not known
	Narrative:
	Mitigation:

Section 4 – Summary and references In addition to the issues highlighted above in relation to specific characteristics, the concept and impact of intersectionality is also of import to this study. Examining the interplay between characteristics and how they may combine to exacerbate equity concerns will be also be part of any equity considerations throughout this project. The impact of intersectionality notwithstanding, it is anticipated that this project will lead to broadly positive impacts for Summary of the main equality issues marginalised groups engaging with the study, due to their overrepresentation in many of the eligibility criteria due to systematic inequity. However, in terms of both the MDFT intervention and the evaluative work surrounding this, there is the possibility of negative consequences in situations where there may be barriers to access for the study. However, as is detailed in the EIA above and the action plan below, actions to mitigate these potential negative impacts will be taken. As well as the collection of data pertaining to the characteristics of participants in the research study by the evaluation team (via collection of relevant protected characteristic data) and the monitoring of data that will be routinely collected by the implementation team (through extraction of this data) the How will the equality impact of the following actions will also be undertaken: study be monitored and evaluated? • Use of this EIA as a basis for subsequent equity focussed discussion of the project, amending and adding to this as necessary as new learning is gained. Completing a formal review of the EIA every 3 months in consultation with the evaluation and implementation teams, alongside input from young people engaged in the advisory group.

